### 10. DATA HANDLING CONVENTIONS

#### 10.1 Derived and Transformed Data

All subjects in the ITT population and Safety Analysis Set will have been randomized. Baseline will be considered as the latest value obtained prior to their treatment start (or randomisation, for any subjects randomised but not treated). Endpoint data will be reported using nominal times related to the treatment start date.

#### **Neurovalens Limited**

Identifier: EXP18020

Clinical Study Identifier: 243973

Percentage weight loss at any nominal time will be calculated as the percentage difference between the weight measurements recorded at baseline, minus the respective time point's weight measurement per subject. Response rate at any time will be calculated as the proportion of subjects who lose at least 5% body weight, with percentage weight loss defined as above.

Similarly, percentage change at any nominal time for other variables will be calculated as the percentage difference between the measurements recorded at baseline, minus the respective time point's measurement per subject.

Prior to performing statistical comparisons, the continuous efficacy endpoints will be evaluated for conformance to parametric assumptions, for example by assessing their distribution, and may be transformed e.g. log transformed if appropriate. If the parametric assumptions cannot be met through transformation, a non-parametric alternative may be used instead.

The laboratory and vital signs data will be recorded using the USA units at each site. As a result, it is not expected that any conversions will be required to standardise data into consistent units.

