## 2.2.2.2 Other secondary endpoints

The efficacy of the VeSTAL device will be evaluated further by performing statistical comparisons between treatment groups on the following secondary efficacy endpoints:

- Percentage trunk fat loss
- Percentage bone mineral content (BMC) gain

The questionaire data, inclusive of the two-day 24-hour dietary recall and modifiable activity questionnaire, will be summarized per treatment group and time point in support of the efficacy findings. Additionally, changes in cardiovascular and initiation of diabetic medications will be summarized in terms of an increase, decrease or no change in concomitant medication. Medications will also be summarized by treatment according to potential impact on weight status. These will be classified as medications that could potentially cause either weight gain or weight loss as deemed by the Chief Investigator.

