### 2.3.2 Support Labeling Claims

The secondary endpoints detailed in Section 2.2.2.1 will be used to support labeling claims and will be tested at the 6 month time point in a sequential order after the primary endpoints. These endpoints will assess the difference between treatment groups by considering the change from baseline to the 6 month time point using a linear model.

The first secondary endpoint that will be tested at 6 months is VAT. An increase in VAT loss, as measured by the whole body DXA scan, will be considered successful if significance is declared with the following statistical hypothesis:

• There is no significant difference between the mean percentage VAT loss of participants using the VeSTAL device and the sham control, i.e.  $\bar{x}_v - \bar{x}_s = 0$ , where  $\bar{x}_v$  and  $\bar{x}_s$  are the mean percentage VAT loss of participants using the VeSTAL device and sham control respectively.

The second secondary endpoint to be tested is LDL. A decrease in LDL will be considered successful if significance is declared with the following statistical hypothesis:

• There is no significant difference between the mean percentage change from baseline in LDL of participants using the VeSTAL device and the sham control, i.e.  $\bar{x}_v - \bar{x}_s = 0$ , where  $\bar{x}_v$  and  $\bar{x}_s$  are the mean percentage change from baseline in LDL of participants using the VeSTAL device and sham control respectively.

The third secondary endpoint to be tested is fat loss. An increase in fat loss, as determined by the whole body DXA scan, will be considered successful if significance is declared with the following statistical hypothesis:

• There is no significant difference between the mean percentage fat loss of participants using the VeSTAL device and the sham control, i.e.  $\bar{x}_v - \bar{x}_s = 0$ , where  $\bar{x}_v$  and  $\bar{x}_s$  are the mean percentage fat loss of participants using the VeSTAL device and sham control respectively.

The fourth secondary endpoint to be tested is lean muscle mass. An increase in lean muscle mass, as determined by the whole body DXA scan, will be considered successful if significance is declared with the following statistical hypothesis:

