• There is no significant difference between the mean percentage change in lean muscle mass of participants using the VeSTAL device and the sham control, i.e.  $\bar{x}_v - \bar{x}_s = 0$ , where  $\bar{x}_v$  and  $\bar{x}_s$  are the mean percentage change in lean muscle mass of participants using the VeSTAL device and sham control respectively.

Identifier: EXP18020 Clinical Study Identifier: 243973

The fifth secondary endpoint to be tested is the atherogenic index. A decrease in the atherogenic index, as determined by the ratio of total cholesterol to HDL, will be considered successful if significance is declared with the following statistical hypothesis:

• There is no significant difference between the mean change from baseline for the ratio of total cholesterol to HDL of participants using the VeSTAL device and the sham control, i.e.  $\bar{x}_v - \bar{x}_s = 0$ , where  $\bar{x}_v$  and  $\bar{x}_s$  are the mean change from baseline in the ratio of total cholesterol to HDL of participants using the VeSTAL device and sham control respectively.

The sixth secondary endpoint to be tested is systemic inflammation. A decrease in systemic inflammation, as measured by high-sensitivity C-reactive protein, will be considered successful if significance is declared with the following statistical hypothesis:

• There is no significant difference between the mean change from baseline for the high-sensitivity C-reactive protein of participants using the VeSTAL device and the sham control, i.e.  $\bar{x}_v - \bar{x}_s = 0$ , where  $\bar{x}_v$  and  $\bar{x}_s$  are the mean change from baseline in the high-sensitivity C-reactive protein of participants using the VeSTAL device and sham control respectively.

The seventh secondary endpoint that will be tested at 6 months is total calorie intake. A decrease in total calorie intake, as measured by the two-day 24-hour dietary recall, will be considered successful if significance is declared with the following statistical hypothesis:

• There is no significant difference between the mean change from baseline for the total calorie intake of participants using the VeSTAL device and the sham control, i.e.  $\bar{x}_v - \bar{x}_s = 0$ , where  $\bar{x}_v$  and  $\bar{x}_s$  are the mean change from baseline of the total calorie intake of participants using the VeSTAL device and sham control respectively.

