 A linear model will be used for the mean percentage fat loss at 6 months having adjusted for covariates of interest: gender and baseline weight. The least square (LS) mean difference between groups will be assessed for a statistically significantly difference from 0 i.e. p-value <0.05.

- Mean percentage change in lean muscle mass;
  - Summary statistics for percentage change in lean muscle mass at 6 months from baseline by treatment group
  - Plotted graphically by treatment group over time
  - A linear model will be used for the mean percentage change in lean muscle mass at 6 months having adjusted for covariates of interest: gender and baseline lean muscle mass. The least square (LS) mean difference between groups will be assessed for a statistically significantly difference from 0 i.e. p-value <0.05.

  - Additional fat and mass endpoints;
    - For each of the following endpoints, comparisons will be performed using a linear model, with the efficacy endpoint at 6 months as the dependent variable and treatment group, gender and baseline value as the explanatory variable.
       Data will also be summarised descriptively over time:
      - Mean percentage trunk fat loss
      - Mean percentage bone mineral content (BMC) gain
- Dietary endpoints;
  - Questionnaire responses, inclusive of those received via the food frequency questionnaire (FFQ) (baseline only) and the two-day 24-hour dietary recall will be summarized per treatment group at baseline and 6 months for the following endpoints:
    - Total Energy Intake (kCal)
    - Carbohydrates (Starchy carbohydrates, sugars and free sugars)
    - Fat and saturated fat
    - Protein
    - Fiber
    - Alcohol

Neurovalens Limited Identifier: EXP18020

Clinical Study Identifier: 243973

A statistical comparison will be performed between treatment groups for the change from baseline in the total calorie intake at 6 months, using a linear model, with the dietary endpoint as the dependent variable and treatment group, gender and baseline calorie intake as the explanatory variables. The two-day 24-hour dietary recall will be used to provide the total calorie intake data at the 6-month time point and baseline. Data will be summarised descriptively and plotted graphically over time.

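### SAP 10.1 computes percentage change as baseline minus follow-up for every variable, which reverses the sign of the LDL, lean muscle mass and bone mineral content estimates

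*SAP*

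**What the plan says.** SAP section 10.1 starts with the primary variable: "Percentage weight loss at any nominal time will be calculated as the percentage difference between the weight measurements recorded at baseline", less the weight at the time point. The next paragraph extends this to the rest: "percentage change at any nominal time for other variables will be calculated as the percentage difference between the measurements recorded at baseline". The same sentence goes on to fix the order of subtraction: "between the measurements recorded at baseline, minus the respective time point". The scope is all other variables, and no endpoint is exempted.

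The endpoints caught by this rule are named in different ways. Section 2.2.2.1 lists, in test order, VAT loss (1), percentage change in LDL (2), fat loss (3) and percentage change in lean muscle mass (4). The remaining labelling endpoints (5 to 8) are absolute changes. Section 2.2.2.2 adds percentage trunk fat loss and "Percentage bone mineral content (BMC) gain". Protocol section 18.3 also lists lean mass and bone mineral content as gains.

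Section 2.3.2 gives the favourable direction in words. For lean mass: "An increase in lean muscle mass, as determined by the whole body DXA scan, will be considered successful if significance is declared". For LDL the favourable direction is a decrease. The hypothesis itself has no direction: "There is no significant difference between the mean percentage change in lean muscle mass of participants using the VeSTAL device and the sham control", written as a difference of zero. The analysis in section 12.1.3 is likewise undirected: "A linear model will be used for the mean percentage change in lean muscle mass at 6 months", adjusted for gender and baseline, with the LS mean difference tested against zero at p<0.05.

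**The concern.** A variable called a gain, or a change from baseline, is normally read as follow-up minus baseline, so that a rise is positive. Section 10.1 gives it the opposite sign. A programmer who follows the SAP exactly will produce LDL, lean-mass and bone mineral content estimates whose signs contradict their labels.

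Two of the three support labelling claims. Someone reading a table headed percentage change in lean muscle mass, with a positive active-minus-sham difference and a confidence interval above zero, would naturally take it as more lean mass on the active device when it means more lean mass lost. For LDL, a favourable result would look like a rise. LDL stands second in the fixed sequence of section 9.4, so a misreading there would also affect whether claims 3 to 8 are examined.

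**Working it through.** No sample size, power or alpha figure in the plan depends on this formula, so there is no stated figure to reproduce. The check applies the rule to each endpoint it covers.

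**Formulas.** The SAP does not state the denominator; baseline is assumed.

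- SAP 10.1: 100 × (baseline − follow-up) / baseline
- Conventional change: 100 × (follow-up − baseline) / baseline

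**Illustrative values (invented; the sign does not depend on them).**

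| Endpoint | Baseline → 6 months | SAP 10.1 | Conventional | SAP sign fits the endpoint name? |
|---|---|---|---|---|
| VAT loss | 1000 → 900 | +10.0% | −10.0% | yes |
| LDL change | 130 → 117 | +10.0% | −10.0% | no |
| Lean mass change | 50 → 51 kg | −2.0% | +2.0% | no |
| Lean mass change | 50 → 49 kg | +2.0% | −2.0% | no |
| BMC gain | 2500 → 2525 g | −1.0% | +1.0% | no |

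For example, lean mass 50 → 51 kg gives 100 × (50 − 51)/50 = −2.0. Fat and trunk fat are also named as losses, so, like VAT, they are correctly signed.

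**Effect on the test.** Reversing the sign of the outcome turns the treatment coefficient b into −b and leaves its standard error unchanged. The t statistic changes sign only, so the two-sided p-value is identical and the interval is mirrored about zero.

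**Illustration with the planned model.** One simulated lean-mass dataset had 90 subjects per arm and a linear model with group, gender and baseline. Assumed true means were −1.5% on active and −0.5% on sham, with SD 3%, so the active arm truly loses more lean mass.

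- SAP 10.1 formula: active minus sham +1.53 (95% CI 0.72 to 2.35), p = 0.0003
- Conventional formula: active minus sham −1.53 (95% CI −2.35 to −0.72), p = 0.0003

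**Is an unfavourable lean-mass difference plausible?** SAP section 5 assumes mean weight losses of 6.6% and 3.1% at a median weight of 90 kg, so the extra loss on active is 0.035 × 90 = 3.15 kg. If 10% to 30% of that were lean tissue (an assumption), the difference would be about 0.3 to 0.9 kg, or 0.6% to 1.9% of an assumed 50 kg lean mass. With SD 3% and 90 per arm, the standard error is 3 × √(2/90) = 0.45, so differences above about 0.9% would reach p<0.05. The sign could therefore matter on a significant result.

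**The case against.** The strongest reply is that the SAP's success rule does not rest on the sign of a derived variable. Section 2.3.2 speaks of an increase in lean muscle mass as measured by DXA, and of a decrease in LDL. A larger lean-mass loss on active is not an increase in lean mass under any coding. Section 9.4 lets the sequence go on only if the criterion for each earlier endpoint has been met, and read with section 2.3.2 that criterion has a direction. Section 12.1.3 also requires observed absolute values and changes for all efficacy outcomes, with plots over time for lean mass and LDL, so a reversal should be seen. These points stand.

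They rule out a stronger inference that a reader might draw: that a significant lean-mass loss on active would satisfy the fourth claim and open the fifth test. The documents do not support this. It would require reading the coefficient's sign while ignoring both the declared coding and the words of section 2.3.2. The inference fails for bone as well, because bone mineral content is neither a labelling endpoint nor subject to any success rule; there the problem is only a gain reported with a minus sign.

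It can also be said that the carry-over in section 10.1 is careless drafting, since sections 2.3.2 and 12.1.3 speak of change from baseline in the usual sense. That is probably so, but it confirms that the SAP contradicts itself. Section 10.1 is the only place that gives a formula, and it is the one a programmer would follow.

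**Conclusion.** The point holds as a wrong derivation with a limited consequence. Following section 10.1 as written reverses the sign of the estimates and confidence intervals for three endpoints: two that support labelling claims (LDL and lean muscle mass) and one other secondary endpoint (bone mineral content). Two-sided p-values, interval widths and effect sizes in absolute terms are unchanged, and the primary endpoint and the endpoints named as a loss are correct. What is at risk is misreading of reported results, not the type I error of the labelling sequence.

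The finding rests on reading the section 10.1 sentence literally, and on baseline being the denominator; any positive denominator gives the same signs. The numerical examples and the SD of 3% are assumptions used only to illustrate. This is a minor correction, worth making because two labelling endpoints are affected.

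**What to change.** In section 10.1:

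- Keep 100 × (baseline − follow-up)/baseline only for endpoints named as a loss: weight, VAT, fat and trunk fat.
- Define 100 × (follow-up − baseline)/baseline for LDL, lean muscle mass and bone mineral content.
- Define the absolute changes (atherogenic index, hs-CRP, calorie intake, quality of life) as follow-up minus baseline. The SAP gives no formula for them at present.

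As a clarification in sections 2.3.2 and 9.4, state which sign of the active-minus-sham difference meets each labelling criterion: positive for VAT loss, fat loss and lean muscle mass; negative for LDL, atherogenic index, hs-CRP and calorie intake; and for quality of life, the sign that means improvement under the scoring used. This mostly puts the existing words of section 2.3.2 in testable form.

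The cost is SAP wording, plus a sign change in any derivation code already written for the three variables. No new data, sample size or alpha change is needed.

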### 10.2 Premature Withdrawal and Missing Data

All subjects enrolled into the study who meet the requirements for the ITT or Safety Analysis Set population will be included in the final analyses. This will include those subjects who withdrew from the study prematurely or have missing data.

For the large part, subjects will contribute what data they have available without imputation. However, for the primary efficacy endpoint of total body weight loss, three approaches to missing or incomplete data will be taken, under the assumption that the data is missing at random:

- 1. Multiple imputation will be applied by means of a multiple imputation model which is composed of three steps:
  - 1.1. The missing data are imputed multiple times to generate multiple sets of data. The imputed values are predicted total body weight loss values obtained from a linear regression model with observed total body weight loss data as the dependent endpoint, and the same covariates of interest that are used to adjust the primary endpoint (treatment group, gender and baseline weight). By providing 75 imputations per missing value, the variability between imputed values represents the uncertainty over the missing value.
  - 1.2. The 75 complete datasets are analyzed using the planned statistical analysis as per section 12.1.1. The results from the 75 complete datasets are then combined to produce an estimate for the primary endpoint, which reflects the uncertainty due to the missing values.
- 2. Last Observation Carried Forward (LOCF) will be applied for all subjects without data, inclusive of those who have withdrawn from the trial and subjects who have not reached the time point.
- 3. Baseline Observation Carried Forward (BOCF) will be applied for all subjects without data, inclusive of those who have withdrawn from the trial and subjects who have not reached the time point.

## Neurovalens Limited

Clinical Study Identifier: 243973

Identifier: EXP18020

The multiple imputation method will be considered primary, with the analyses using LOCF and BOCF imputation considered supportive. These methods will be applied to missing data at 6 months and also at 3 months for use in the repeated measures model. A separate multiple imputation model will be fitted for each time point.

For the binary weight loss endpoint, subjects who have missing data and withdrew due to adverse events or a change in medication will be considered non-responders in all analyses. Other subjects with missing data will use their imputed weight value to determine response status.

Additionally, a sensitivity analysis will be performed with the binary weight loss endpoint. This analysis will include a best-case scenario, assuming subjects with missing values (and that did not withdraw due to adverse events or change in medication) have all lost over 5% body weight if randomized to VeSTAL device and not lost over 5% body weight if randomized to sham control, and a worst-case scenario, assuming no such subjects with missing values have lost over 5% body weight if randomized to VeSTAL device and all lost over 5% body weight if randomized to sham control. If the best and worst case scenario imputations provide conflicting conclusions i.e. straddle p=0.05 then a tipping point analysis will be used to determine the proportion of values imputed with the best or worst case scenario at which the level of imputation changes the significance of the binary weight loss criterion (as described in Yan et al., 2009).

For adverse events which have missing or partial start dates, and it is unclear as to whether the AE (or ADE) is treatment emergent, the worse-case scenario will be assumed to categorise the AE (or ADE) as treatment emergent.

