### 6.2 Summary of Site Visit 2 (3 months)

### Measurements and Assessments During Visit 2

Vestibular Stimulation to Trigger Adip Clinical Trial Project Name	34 of 112		
Clinical Protocol for VeSTAL			
243973(NI)_181094(UCSD USA) Study Reference Number	Protocol Document Type	01 Document Number	11 Revision Number

- Urine pregnancy test (if applicable)
- Visual check skin behind ears
- Weight (Must be conducted with the participants wearing underwear and a hospital gown only this must be consistent throughout the study duration. They should also have an empty bladder. Weight will be taken on calibrated scales at study site, and calibration records will be reviewed during monitoring visits.)
- Completion of adverse event questionnaire by subject
- Dietician to assess diet via a two-day 24-hour dietary recall.

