## 12. ANALYSIS CORRESPONDING TO THE STUDY OBJECTIVES

### 12.1 Efficacy

The clinical performance of the VeSTAL device, in comparison to the sham control device will be evaluated using efficacy analyses performed on the ITT analysis population and categorised as

Neurovalens Limited Identifier: EXP18020

Clinical Study Identifier: 243973

primary, supportive and secondary efficacy. The primary efficacy analysis results, in combination with the supportive efficacy analysis results will be utilized to consider the success of the study.

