### 12.1.2 Supportive Primary Efficacy Analyses

For the purposes of the *USA regulatory clearance pathway*, the number and percentage of people achieving a loss of at least 5% of their body weight by the 6 month time point in the VeSTAL device treatment group will be presented with a two-sided 95% exact binomial confidence interval for the response rate. The criterion for success is that the lower bound of the 95% confidence interval of the response rate in the VeSTAL device group exceeds 50%. The analysis will use the multiple imputation for missing data as primary, with the LOCF and BOCF imputation methods as supportive.

A Fisher's exact test will also be used to compare the response rates in each treatment group and to detect whether the difference between groups is statistically significant. This will be repeated using multiple imputation, LOCF and BOCF methods for missing data. For the multiple imputation-based analysis, the median p-value approach will be used to generate the Fisher's exact test p-value (Eekhout 2017) and the exact confidence intervals described above will be produced using the imputation with a p-value equal to or nearest the median p-value.

In addition, a sensitivity analysis will be performed with the binary weight loss endpoint, to assess the impact of imputing the best and worst case scenarios for the binary response, when the total body weight loss at 6 months is missing. As per section 10.2, a tipping point analysis will also be utilised to demonstrate the level of imputation which changes the significance of the binary weight loss criterion.

No supportive primary efficacy analyses are required for the *EU regulatory clearance pathway*.

Identifier: EXP18020 Clinical Study Identifier: 243973

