## 12.1.3 Secondary Efficacy Analyses

For both the *EU and USA regulatory clearance pathways*, secondary efficacy analyses will be performed to investigate the difference between treatment groups (using multiple imputation, LOCF and BOCF for missing data for weight outcomes, observed data for other outcomes) in:

- Mean percentage weight loss;
  - A t-test will be used to detect a statistically significant difference (p-value < 0.05)

     between the mean percentage weight loss per group (unadjusted analysis).
  - The mean percentage weight loss between groups, having accounted for covariates of interest and repeated measures over time. In order to do so, a mixed effect repeated measures (MMRM) model will be developed using percentage weight loss at 3 and 6 months) and controlling for the prespecified covariates of interest: gender and baseline weight. Subject will be included in the mixed effects model as a random effect with an unstructured covariance structure. If a convergent model cannot be achieved with an unstructured covariance, further covariance structures will be tested sequentially until a satisfactory model has been achieved.
  - Plot of the Ismeans of change from baseline at 3 and 6 months obtained from the MMRM analysis described above with MI for missing data only
- Adjusted response rate;
  - o whereby response is defined as a subject achieving a percentage weight loss of at least 5% by 6 months. The adjusted response rate will be obtained by means of a logistic regression model with a binary response indicator as the dependent variable, treatment group as the explanatory variable and adjusting for covariates of interest: gender and baseline weight.
- Mean percentage VAT loss;
  - Summary statistics for percentage VAT loss at 3 and 6 months from baseline by treatment group
  - o Plotted graphically by treatment group over time
  - A linear model will be used for the mean percentage VAT loss at 6 months having adjusted for covariates of interest: gender and baseline VAT. The least square (LS) mean difference between groups will be assessed for a statistically significantly difference from 0 i.e. p-value <0.05.

- Mean percentage fat loss;
  - Summary statistics for percentage fat loss at 3 and 6 months from baseline by treatment group
  - Plotted graphically by treatment group over time

Neurovalens Limited Identifier: EXP18020

Clinical Study Identifier: 243973

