## 13. CHANGES OF ANALYSIS FROM PROTOCOL

The analyses contained within this statistical analysis plan supersedes the analyses defined in the study protocol (May 26th 2019, Version 5). For clarity, a summary of deviations from the protocol are summarized, along with justification for the change.

Neurovalens Limited Identifier: EXP18020

Clinical Study Identifier: 243973

1. All terminology reference to treatment dose has been removed as subjects will not receive a specific dose of treatment, but rather use the device headset as demonstrated. The dose response analysis described in the protocol will be reference as a treatment response analysis within this statistical analysis plan and related documents thereafter. Additionally, the treatment response analysis (section 12.3) will be performed on the safety analysis set to reflect the treatment that subjects actually received as opposed to the Intention to treat population referenced in the protocol which reflects randomized treatment.

- 2. The protocol references using usage time as a covariate in the linear modelling of percentage fat loss from baseline. As a post baseline endpoint, it may be difficult to distinguish the relationship between percentage fat loss and usage time, due to a cause and effect relationship e.g. the subject may discontinue treatment as they think the treatment is not effective, which in turn means that their percentage fat loss is reduced. As a result, only baseline covariates will be used to adjust the percentage fat loss from baseline, in the same way that percentage weight loss from baseline is treated. As an alternative means of investigating the relationship between usage time and percentage weight or fat loss, a descriptive summary will be provided for weight and fat loss by categorical groups of usage adherence.

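### The primary imputation of 6-month weight loss ignores the 3-month weight the trial collects, so the single-arm responder rate can shift with early dropout

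*SAP*

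**What the plan says.** SAP section 10.2 makes multiple imputation the primary method, under a missing-at-random assumption. Imputed values come from a linear regression on "the same covariates of interest that are used to adjust the primary endpoint (treatment group, gender and baseline weight"). The same section states: "A separate multiple imputation model will be fitted for each time point". The covariate list in Protocol section 34.1 (Missing Data) is different, but it also lacks the 3-month weight.

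That weight is available. Protocol section 6.2 schedules it at Visit 2, and SAP section 12.1.3 uses it in a secondary analysis, where "a mixed effect repeated measures (MMRM) model will be developed using percentage weight loss at 3 and 6 months".

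The imputed weight also decides responder status. The exception is that "subjects who have missing data and withdrew due to adverse events or a change in medication will be considered non-responders in all analyses". For the US response-rate criterion, SAP section 12.1.2 says: "The analysis will use the multiple imputation for missing data as primary". LOCF and BOCF are supportive. Best-case, worst-case and tipping-point analyses are sensitivity analyses.

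**The concern.** With these predictors, missing at random holds only if dropout is unrelated to early weight loss, given group, gender and baseline weight. In a weight-loss trial, early loss is the obvious variable to condition on. SAP section 13 itself gives the example that "the subject may discontinue treatment as they think the treatment is not effective". That remark concerns usage time and fat loss, and stopping treatment is not the same as a missing 6-month weight: Protocol section 20.6 asks leavers for a weight, optionally. It shows the mechanism was thought plausible, not that it will occur.

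The responder criterion is the exposed endpoint because it is judged in the active arm alone, so a shift common to both arms does not cancel. If poor early losers leave more often, the planned model gives them average outcomes and the rate is inflated. If good early losers leave, the rate is biased down and the sponsor loses power.

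**Working it through.** **The plan's own figures.** 180/(1 − 0.10) = 200, as stated. With mean 6.6 and SD 3.9, the planned responder rate is Φ((6.6 − 5)/3.9) = 65.9% if loss is normal. The responder rule alone has 85.8% power at 90 per arm (55/90 needed). For the mean criterion (lower limit above 2), the adjusted SD is 3.9 × √(1 − 0.16) = 3.57, giving 80.4% power. Joint power is then about 72% at 90 per arm and 76% at 100, so the stated figure of more than 80% is not reproduced. It is reproduced (85.6%) if the mean criterion is an observed difference of at least 2 with p ≤ 0.05. That is a separate matter and does not affect this point.

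**The two models for 6-month loss Y6.**
- Planned: Y6 on group, gender, baseline weight.
- Sequential: Y3 on group, gender, baseline weight; then Y6 on the same variables plus Y3.

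**Inputs from the documents.** 100 per arm randomized, 10% dropout, SD 3.9, baseline weight log-normal (median 90 kg, CV 24%), correlation with loss −0.4, control mean 3.1, 75 imputations, exact interval from the imputation nearest the median Fisher p-value. Success needs 61/100 (lower limit 50.7%; 60/100 gives 49.7%).

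**Assumed, not in the documents.** All dropout after month 3; 3/6-month residual correlation 0.8; month-3 mean 60% of month 6, SD 2.8; dropout sampling weight 1.75 (moderate) or 3.1 (strong) per SD lower month-3 loss; 30% of dropouts fall under the non-responder rule. The true active rate is set at 50%. Under moderate or strong selection, active dropouts average 1.6% or 0.3% loss at month 3, against 3.0% overall.

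**Results** (8,000 simulated trials per setting; Monte Carlo SE about 0.2 points for false success):

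| Selection; share under rule | Planned: rate / false success on responders / on both | With month 3: rate / responders / both |
|---|---|---|
| Moderate; 30% | 50.0% / 1.8% / 0.3% | 49.0% / 1.0% / 0.2% |
| Strong; 30% | 51.2% / 3.7% / 0.5% | 49.3% / 1.1% / 0.2% |
| Moderate to strong; none | 51.5–52.8% / 4–7% / 0.5–0.9% | 50.0–50.1% / about 2% / – |
| Good losers leave, 1.75; none | 48.5% | 50.0% |
| Good losers leave, 1.75; 30% | 46.8% | 47.9% |

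**Reading the first row.** The planned 50.0% only looks right. The non-responder rule makes the target a composite rate, which is below 50%. The drop of 50.0 − 49.0 = 1.0 point is three subjects per 100, about a third of whom would have responded. The planned model adds about 1.0 point of imputation error, which happens to cancel that drop. Against the composite target, a rerun put the planned model's error at about +1.0 (moderate), +1.9 (strong) and −1.0 (opposite direction), and the sequential model within 0.1.

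**Check by arithmetic.** Shift = dropout × (1 − share under rule) × (imputed minus true response rate among dropouts). With no one under the rule, 51.5 − 50.0 = 1.5 points at 10% dropout implies a 15-point gap. With 30% under the rule, 0.10 × 0.70 × 15 = 1.05, against 50.0 − 49.0 = 1.0 simulated. Strong: a gap of 28 gives 0.07 × 28 = 1.96, against 51.2 − 49.3 = 1.9.

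**Separate large-sample check** at the planned 65.9%, 10% dropout, correlation 0.6 to 0.9, log-odds 0.7 to 1.5 per SD, nobody under the rule: shift +1.2 to +3.8 or −1.0 to −2.5 points, and 0.0 once 3-month loss is used. If only half of dropouts have a 3-month weight, about half the shift remains.

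**Other consequences.**
- Random dropout, true difference 3.5: SE 0.538 planned against 0.520; power on the mean criterion about 78% against 81%.
- Mean difference: 3.5 if dropout acts alike in both arms; 3.65 if only active dropout depends on early loss, 3.36 if only control (both 1.75).
- Separate imputation by visit lowered the 3/6-month correlation in the completed data from 0.83 to 0.72–0.75, which weakens the repeated measures analysis. Sequential imputation restored 0.83.

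**The case against.** The strongest reply is that no decision changes. US success needs both criteria. A 50% responder rate corresponds to an active mean near 5.0, so the difference from a control mean of 3.1 is only 1.9 and the mean criterion blocks most false passes. Joint false success is 0.3% against 0.2% in the central case. It passes 2.5% only if the control mean is below plan: 3.2% at 1.5 with strong selection and 30% under the rule; with nobody under the rule, 3.6% at 2.5 with strong selection, or 4.0–6.5% at 1.5. The EU pathway has no responder criterion. This stands, and it keeps the point minor.

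The size also rests on assumptions. Direction is unknown, and having all dropout after month 3 favours the change. With half of it earlier, the central correction shrinks to 50.0% against 49.5%. Visits missed because of COVID-19 may be unrelated to early loss. This also stands.

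The change can lower apparent power: in the central direction at the planned effect, joint power is 72.6% planned and 69.9% with month 3. That is inflation removed. If good losers leave (30% under the rule), it rises from 60.0% to 66.3%.

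Finally, the planned sensitivity analyses can expose a problem, and SAP section 12.1 says the primary results "in combination with the supportive efficacy analysis results will be utilized to consider the success of the study". But no decision rule is given and none of them corrects the primary estimate. LOCF fails in 81–84% of the planned model's false successes, but also in 20–23% of its passes at the planned effect, so a conflict does not tell the two apart. The check of missing completely at random in Protocol section 34.1 does not alter the imputation model.

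**Conclusion.** The concern holds as an optional improvement. The omission is certain from SAP section 10.2, and nothing elsewhere in the plan repairs it. Its size is conditional. At 10% dropout the responder rate shifts by roughly 1 to 4 points if dropout follows early loss, in either direction, and not at all if it does not. Responder false success reaches 3.7% under strong selection with 30% under the rule, and 4–7% with nobody under it. Joint false success stays below 1% at the planned control mean. The between-arm mean difference is unbiased if dropout acts alike in both arms. The sign of the baseline correlation (−0.4 in the protocol, 0.4 in SAP section 5) hardly matters: +0.4 gives 50.1% and 2.0% in the central case. The precision gain does not depend on selective dropout.

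**What to change.** In SAP section 10.2, replace the separate models with one sequential imputation: monotone regression, or fully conditional specification where gaps are intermittent. Impute month-3 loss from treatment group, gender and baseline weight, then month-6 loss from the same variables plus month-3 loss. Use the same imputed datasets for the continuous, responder and repeated measures analyses. Keep the non-responder rule and all sensitivity analyses, because subjects lost before month 3 gain nothing from this change.

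The cost is SAP wording and one extra predictor, with no new data or visits. Because Protocol section 34.1 ties the imputation covariates to those of the regression, add an entry in SAP section 13. SAP section 1 says version 1.1 was agreed with FDA, so the change may also need to be raised there. It should be made before unblinding.
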